8.6 Blood collection and DBS preparation

DBS samples are produced from EDTA capillary blood samples for each survey participant with positive results of the third HIV rapid test, and for 10% participants with HIV-negative result of the first rapid test, selected randomly in each city of survey, as well as for those participants who stated they are receiving ART in their questionnaires (Annex 23. DBS registration form).

One Whatman 903 Protein Saver Card (EU) DBS card should be filled with at least with 75 µl of blood

per circle. Sterile disposable pipettes with appropriate calibration are used to transfer a blood sample from a container with EDTA capillary blood to DBS card. It's necessary to turn the EDTA container 20 times before sample transfer. All other stages of DBS preparation must be carried out in accordance with the procedure specified in the relevant SOPs. The survey site healthcare worker will be trained in accordance with the CDC's instructions for this procedure; his/her competence will be checked by the national coordinator. The DBS cards are identified by a survey identification number and dried on a grid at room temperature at the testing sites. After drying, the cards are packed into hermetically sealed packages, along with the humidity indicator and the dryer, and forwarded to the Reference Laboratory for HIV/AIDS diagnostic (each new batch is forwarded in 10 days) by a transport service that guarantees the appropriate temperature conditions.

All test results are entered into the Test Results Form (Annex 15. Test Results Form).

8.7 Laboratory testing

All DBS samples are tested for recent infection and viral load (VL) in the Reference Laboratory for HIV/AIDS diagnostic in accordance with the testing algorithm and SOPs (Annex 24. Form of routine forwarding of the DBS samples to the Reference Laboratory).

Results of confirmed recency test will not be returned to patients. Results of VL will be returned by the lab to each site coordinator, who in turn will hand them over to local HIV clinics to which participants will be redirected. A medical specialist informs participants about the possibility of obtaining their results after they have been processed by the laboratory and received by the HIV clinics.

The quality of DBS cards is checked before testing (Annex 22. Form of rejected DBS registration). The cards are not tested if: there is a blood clot on a paper; blood is applied on both paper sides; insufficient amount of blood to cover the circles with 15 mm diameter; blood from different circles merged into one spot; serum separated from thrombocytes on a paper and created light circles around them; blood spots are blurred and not-colored; samples were not dried completely before transportation (intensive red spots); there are signs of rotting and mycotic DBS damage.

All HIV-positive DBS samples are tested as to recent infection (Maxim HIV-1 EIA Lag-Avidity EIA for Dried Blood Spots) and viral load (Abbott Real Time HIV-1 Test). Samples with $VL \geq 1000$ copies/ml are considered to be the confirmed cases of recent HIV-1 infection. Samples with $VL \leq 1000$ copies/ml are classified as long-term infection.

If the test is not performed correctly, an additional test is performed using the already collected sample (in a tube with anticoagulant). Additional blood is not collected. All residual samples are disposed of as corresponding category B in accordance with the order of the Ministry of Health of Ukraine dated June 9, 2022 No. 1602 On approval of changes to the State Sanitary and Epidemiological Rules and Norms for the Management of Medical Waste (<https://zakon.rada.gov.ua/laws/show/z1387-22#Text>)

All samples are destroyed and not used for future testing.

As of December 2020, RTI (i.e., HIV recency tests) have not been pre-qualified by the World Health Organization or approved by the U.S. Food and Drug Administration (FDA) for clinical use and are being used primarily for surveillance."

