14.8	Protocol deviations.....	52
14.9	Potential benefits	52
14.10	Compensation.....	52
14.11	Age of respondents.....	52
15.0	STUDY TIMELINE	55
16.0	Annex. Selection of cities for the 2023 PWID IBBS	56

LIST OF ACRONYMS AND DEFINITIONS

AIDS	acquired immunodeficiency syndrome - a chronic, potentially life-threatening condition caused by the human immunodeficiency virus
ART	antiretroviral therapy - the use of HIV medicines to treat HIV infection
Behavioral component	survey of behavioral factors by means of a face-to-face interview method - direct communication between the interviewer and the respondent
Biological component	testing of respondents for HIV infection, hepatitis C and syphilis, as well as pre-test and post-test counseling
CDC	Centers for Disease Control and Prevention
DBS	dry blood spot
GAM	UNAIDS Global AIDS Monitoring
HCV	hepatitis C - an infectious disease caused by the hepatitis C virus that primarily affects the liver
HIV	human immunodeficiency virus infection
HTS	HIV testing services - voluntary medical testing of this person for the presence of HIV antibodies
IBBS	Integrated Biological and Behavioral Surveillance – a methodology using cross-sectional surveys with behavioral and biological components that are linked at the respondent level
KI	key informants - representatives of NGOs or private persons with expert knowledge of the survey target group
MOH	Ministry of health of Ukraine
MSM	men who have sex with men
NGO	non-governmental organization - legalized or registered according to the legislation of Ukraine
PLHIV	people living with HIV
PrEP	pre-exposure prophylaxis - an HIV prevention strategy when HIV negative individuals take anti-HIV medications before coming into contact with HIV to reduce their risk of becoming infected
Primary respondents (seeds)	survey participants, recruited by the NGOs according to the criteria set, being the beginning of other responders' recruitment chain
PSE	population size estimation
PWID	people who inject drugs
RDS	respondent-driven sampling
Recruiter	survey participant recruiting other potential responders among the representatives of the survey target group
RITA	The Recent Infection Testing Algorithm - a generic name for a sequence of laboratory methods to distinguish recent HIV infections from HIV infections which have been present for some time
RT	rapid testing
Secondary respondents	survey participants invited by other PWID who have participated in all components of the survey

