9.5 Estimation of HIV incidence

The biological component of the IBBS will provide estimates of recent HIV infection and viral load, to be used for calculation of HIV incidence among PWID.

A new method for calculating annual incidence¹⁴ will be used. The corresponding method was implemented in the package "inctools" (version 1.0.15) for R. This approach has been previously reviewed and approved by international experts and statistics specialists.

The report on the IBBS findings will include a median incidence estimation and interquartile range observed in different cities among PWID, allowing for understanding the variability across the different regions of the country.

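### Section 8.7 leaves the LAg-Avidity result out of its definition of recent HIV infection, so the rule as worded separates samples on viral load alone

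*Protocol*

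**What the plan says.** Section 8.7 of the protocol first sets the testing: "All HIV-positive DBS samples are tested as to recent infection" with the Maxim LAg-Avidity assay for dried blood spots, and the same samples get an Abbott viral load. Two classification sentences follow. Samples with a viral load at or above 1000 "copies/ml are considered to be the confirmed cases of recent HIV-1 infection". Samples with a viral load at or below 1000 "copies/ml are classified as long-term infection".

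Section 9.5 relies on this result: "The biological component of the IBBS will provide estimates of recent HIV infection and viral load, to be used for calculation of HIV incidence". It names the general biomarker-based estimator and the inctools package, and does not restate the case definition. Estimating HIV incidence is one of the objectives in Section 3.0.

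Two other places bear on the intent. Section 8.7 opens by saying that samples are tested "in accordance with the testing algorithm and SOPs". The list of acronyms defines RITA as "a generic name for a sequence of laboratory methods to distinguish recent HIV infections from HIV infections which have been present for some time".

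**The concern.** The classification sentences directly follow the one that puts all HIV-positive samples through both assays, and neither is limited to samples that were recent on LAg. Read as written, the LAg result is produced and then not used. A person infected years ago who is untreated or not suppressed would be recorded as a confirmed recent infection. The two classes also meet at exactly 1000 copies/ml, although few samples will sit there.

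The count of recent infections is the numerator of the incidence estimate. Under the literal rule, recent becomes the complement of a viral load below 1000, so incidence and viral suppression would be one measurement reported twice. Better suppression between rounds would look like falling incidence. The median and interquartile range of incidence across cities promised in Section 9.5 would partly reflect how well each city suppresses.

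**Working it through.** **Inputs from the protocol.** Section 4.4: prevalence 21%, suppression 44%, design effect 3.0, 5% missing, half-width 7 points, sample size 2914, 500 per city (six sentinel cities, so 3000), 629 HIV-positive, and a trend target of 52% suppression. Section 2.0: 350,500 PWID, about 71,000 of them HIV-positive, 5960 injecting-related registrations in 2020, and a 1.5-fold under-ascertainment of such cases.

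**Assumptions, not in the protocol.** Suppression means viral load below 1000 (no cut-off is given). Mean duration of recency is 130 to 200 days. The false-recent rate is 0 unless stated.

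**1. Reproduce the plan's own figure.** HIV-positive participants needed = 1.96² × 0.44 × 0.56 × 3.0 / 0.07² = 579.5. Dividing by 0.21 gives 2760, and by 0.95 gives 2905, against 2914 stated. The inputs are therefore read correctly. Also 0.21 × 3000 = 630, against 629 stated.

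**2. Count labelled recent by the literal rule.**
- After 5% missing: 3000 × 0.21 × 0.95 = 598.5 HIV-positive; × 0.56 = 335 recent.
- With the protocol's 629: 629 × 0.56 = 352 recent.

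**3. Implied incidence.** With a false-recent rate of 0, the estimator is recent cases / (HIV-negative participants × mean duration in years).
- HIV-negative: 3000 × 0.79 × 0.95 = 2251.
- 130 days: 335 / (2251 × 130/365) = 41.8 per 100 person-years.
- 200 days: 335 / (2251 × 200/365) = 27.2 per 100 person-years.
- Using 352 recent and 629 × 0.79/0.21 = 2366 HIV-negative gives the same 41.8, because the missing-data factor cancels.

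**4. Sensitivity to suppression.** The Section 4.4 table shows 68.8% to 90.9% for the five sentinel cities it covers; the Annex shows 20.0% to 62.1% for the same cities. At 82%, near the level of the table: 629 × 0.18 = 113 recent, and 113 / (2366 × 130/365) = 13.4 per 100 person-years.

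**5. Sensitivity to the false-recent rate.** With rate e and a one-year cut-off, incidence = (R − e × N+) / (N− × (mean duration − e)). At 130 days and 44% suppression, e = 1% gives 42.3 and e = 2% gives 42.7.

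**6. Scale from the protocol itself.** HIV-negative PWID: 350,500 − 71,000 = 279,500. Then 5960 / 279,500 = 2.1 per 100 per year, or 3.2 after multiplying by 1.5. At 130 days the literal rule is 13 times (41.8/3.2) to 20 times (41.8/2.1) that at 44% suppression, and about 4 times (13.4/3.2) to 6 times (13.4/2.1) at 82%. Registrations are diagnoses, not new infections, so this gives only an order of magnitude.

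**7. Trend effect.** If suppression rises from 44% to 52%, the share labelled recent falls from 56% to 48%. At 130 days, incidence falls from 41.8 to 629 × 0.48 / (2366 × 130/365) = 35.8 with no change in transmission.

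**The case against.** The strongest reply is that a qualifier has dropped out of a sentence and nobody chose to classify on viral load. Calling a case confirmed presupposes an earlier recent result. RITA is defined as a sequence of methods. The section points to a testing algorithm and SOPs, and running LAg on every HIV-positive sample would be pointless if it had no role. Diagram 1 and the SOPs are not shown and may already contain the LAg step. All of this stands. It limits the point to the protocol's wording, and it means no one can say from these documents that the SOP is wrong.

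A reader might infer that every viraemic participant will be counted as recent and that reported incidence will be overstated many-fold. The documents do not support that. It would happen only if the laboratory or the analyst applied the two sentences literally and set aside the LAg results. Even then, detectable viral loads below 1000 are classed as long-term.

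The magnitude is also conditional. A near-zero false-recent rate belongs to a combined LAg and viral-load algorithm; under a rule based on viral load alone it would be large. The 27 to 42 therefore describes literal counts paired with the parameters of the combined algorithm.

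The damage would be reversible: both results exist for each HIV-positive sample tested, so recency can be re-derived. Prevalence, suppression and sample size are untouched. What survives is that the protocol states a case definition, the statement is wrong as worded, and no other text shown corrects it.

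**Conclusion.** The definition of recent infection in Section 8.7 is incomplete and needs correcting before incidence is analysed. The omission of LAg from both conditions and the overlap at exactly 1000 are certain from the text. A bias in reported incidence is not established; it depends on literal use of the rule, and the wording points to a different intent.

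If the rule were used literally, about 56% of HIV-positive participants (335 of 599, or 352 of 629) would be labelled recent at the protocol's 44% suppression. That implies about 27 to 42 per 100 person-years for a mean duration of 200 to 130 days, or about 13 at 130 days if suppression is nearer 82%. These figures rest on the assumed duration, a false-recent rate of 0, and suppression taken as viral load below 1000. Against the rough 2 to 3 per 100 per year from registrations they would be implausible. The exact overstatement cannot be given, because the protocol does not state what share of samples at or above 1000 would be LAg-recent.

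**What to change.** Replace the two classification sentences in Section 8.7 with: *Recent infection = LAg-Avidity result in the recent range, at the cut-off specified for the dried-blood-spot assay, AND viral load ≥1000 copies/ml. All other HIV-positive samples, including LAg-recent samples with viral load <1000 and LAg long-term samples at any viral load, are long-term infection.* The sponsor should enter the cut-off value from the assay's specification. This wording also removes the overlap at 1000.

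Check that the laboratory SOP and Diagram 1 carry the same rule, and change them only if they do not. In Section 9.5, state that the mean duration of recency and the false-recent rate given to inctools are those belonging to this combined definition.

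The cost is two sentences in Section 8.7, one in Section 9.5 and a document check. No new test, sample or visit is needed. If samples have already been classified, recency can be re-derived from the LAg and viral load results on file.

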8.8 Post-test counseling and referral to services

HIV: All respondents undergo post-test counseling in accordance with the National Protocol of the HTS. The participants with HIV-positive result under the second and the third rapid diagnostic tests are informed by healthcare workers about the final result (Annex 17. Certificate of HIV test results) and referred on the same day to the nearest HIV clinic or ART site for ART initiation (Annex 16. Referral form for the survey participant; Annex 20. Registration log for referrals to HIV Clinics). During the data collection phase, representatives of local NGOs providing HIV testing and linkage services to PWID will be present at survey sites, and will enroll newly detected HIV positive participants in their projects, which provide active referral (accompanying) to HIV clinics and extended follow-up. The regional coordinator ensures the presence of social workers from a specialized NGO on the study site to accompany participants. If one social worker will not be enough, the regional coordinator will attract the necessary number of specialists to the site. Additionally, information on the referral to medical institutions, including the HIV clinic, is indicated in the informed consent that is provided to participant when he/she arrives at the site.

In accordance with the national procedure of ART prescription (Order of the Ministry of Health of Ukraine No. 551 of 2010), ART can be initiated immediately after an HIV-positive representative of a key groups is linked to care. The reluctance of HIV-positive participants to be registered with a HCF may be an obstacle to starting treatment the same day. Therefore, the specialized projects provide extended follow-up to ensure linkage to care when participant is ready for this.

If present in the city, additional referrals will be provided to social care and support projects (Annex 19. Social support referral form for the survey participant).

In case of HIV negative result all PWID who tested negative will be informed about PrEP options, which are available for free at the nearest HIV clinic/ART site. They will be offered to be accompanied by the social worker for PrEP initiation.

In case of a positive result of an HIV test, a medical specialist will also provide information on recent/long-term HIV infection, consequences for the health of participants, preventive activities for participants and their family members and social environment (Appendix 35 Fact sheet on understanding recent and long-term HIV infection). Also, a medical specialist will inform the participants that they will be able to obtain their results after processing by the Reference Laboratory for HIV / AIDS diagnostic by contacting the AIDS Centre in their city and giving the ID number that is indicated in the referral (Annex 16 Referral for the participant of the study).

Tracking of HIV clinic referral outcome will be done by the social worker of the specialized NGO using the Referral Log (Annex 20). Two weeks after the end of the field stage, the Regional Coordinator will aggregate and submit the information on the number of participants who have visited the HIV clinic and who have started the ARV-treatment or PrEP to the central study team.

Hepatitis C: According to the national guidelines on Hepatitis C, diagnosis is made based on the results of laboratory testing. In case of a positive screening rapid test result for anti-HCV, the participant is consulted on possible viral infections and the need for follow-up examination. Participants with positive result will be referred to:

- HIV clinic (in case of HIV/viral hepatitis co-infection),
- family doctor,

- infectious diseases physician at a clinical diagnostic center at the place of their residence,
- infectious diseases physician at a specialized department of clinical hospital at the place of their residence.

At the stage of formative assessment, the Regional Working Group members, in particular, regional coordinator and the representatives of HIV clinics, will make up an up-to-date list of facilities that provide HCV diagnostic and treatment referral, as well as available projects that may cover the diagnostic costs. Participants who test positive for HCV antibodies and do not self-report having been treated for HCV will be referred to the identified clinics and projects using the Referral Form (Annex 16), accompanied by the Test Result Form (Annex 18).

To track the referral outcomes, the participants will be asked to provide their phone number. The study team social worker will call these participants two weeks after referral and record the results in the Referral Log (Annex 21). Two weeks after the end of the field stage, the Regional Coordinator will aggregate the data from the Log, and submit the information on the number of people who were successfully linked to a treatment facility. According to the data from the Log, we receive two indicators: 1. the number of PWID, who visited HCF (for consulting and confirmatory testing); 2. the number of PWID who started treatment after HCV PCR testing. Only the second indicator we can consider a successful linkage. All participants will be given informational and promotional materials about the prevention and treatment of the hepatitis C by a coupon manager.

Syphilis: According to the national guidelines on syphilis, diagnosis needs to be confirmed by laboratory testing. In case of a positive rapid screening test result for syphilis, the participant is consulted on possible bacterial infection and the need for diagnostic testing. Participants with positive result will be referred to:

- dermatovenerological dispensary;
- dermatovenerological hospital;
- dermatovenerologist at a clinical diagnostic center at the place of their residence.

At the stage of formative assessment, the Regional Working Group members, in particular, a regional coordinator and the representatives of HIV clinics, will prepare a list of facilities for referral.

Referral will be made using the Referral Form (Annex 16). To track the referral outcomes, the participants will be asked to provide their phone number. The study team social worker will call these participants two weeks after referral and record the results in the Referral Log (Annex 21). Two weeks after the end of the field stage, the Regional Coordinator will aggregate the data from the Log and submit the information on the number of people who were successfully linked to a treatment facility.

9.0 DATA MANAGEMENT AND ANALYSIS

The questionnaire data were exported from PHC_Research to a SPSS datafile, with attached variable and value labels. The questionnaire dataset will be cleaned, recoded, and re-labeled as necessary. The coupon management and biological testing data will be cross-checked, cleaned, and merged with the main survey dataset.

9.1 RDS weighting and diagnostics

To verify RDS assumptions, data will be imported to specialized RDS software (“RDS” package for R or RDS-Analyst). Convergence plots will be constructed to assess whether equilibrium was achieved in each city. Additionally, bottleneck plots and recruitment homophily for key variables of interest will be assessed. Recruitment chain graphics will be constructed to visualize the process of recruitment in each city. This will be done during data collection to inform recruitment (i.e. terminating and adding new chains), as well as during the analysis phase to verify assumptions.

In order to minimize biases inherent to RDS, all descriptive analyses will apply individual RDS network weights calculated using a sampling estimator selected based on the recruitment and sampling characteristics (e.g. the Gile’s successive estimator). The first set of weights will be based on the network size variable (the number of PWID representatives older than 14 years old that the respondent has seen over the past 30 days) as reported by the participants, and an alternative set will be calculated using the imputed visibility produced by the RDS package (to be used in sensitivity analyses).

9.2 Descriptive statistics

Descriptive statistics for all key variables (prevalence of infections, drug use, behaviors, service use, HIV treatment cascade, etc) will include category size (n), population proportions with 95% confidence intervals, means with standard errors or medians with interquartile range. All descriptive statistics including confidence intervals will be calculated using the RDS weights. The total sample estimates will use the RDS weights but will not be additionally weighted due to the equal sample size in each city. When the population size calculation becomes available (see below), additional weighting by population size in each city will be done to obtain estimates for the entire city sample for key variables. Descriptive tables will be disaggregated by city and key demographic characteristics (age group and gender). Visualizations for selected variables and disaggregations will be provided in bar or line charts. The design of tables and charts will take into account the structure of the previous reports on the IBBS findings in Ukraine.

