1.0 SUMMARY

Conceived as a part of second-generation HIV surveillance¹, integrated biological and behavioral surveillance (IBBS), has become a critical element of HIV response in Ukraine. The primary purpose of IBBS is to estimate the burden of HIV disease and HIV-related risk factors, and estimate the coverage of prevention and treatment services for populations at increased risk for HIV. When conducted repeatedly, IBBS allows to evaluate trends in HIV prevalence and other key indicators over time. These data are essential for program planning, implementation, and evaluation.

This protocol describes the methodology of 2023 round of IBBS among people who inject drugs (PWID) in Ukraine. The study is designed as a cross-sectional survey with biological and behavioral components. The survey sample will be recruited using respondent-driven sampling (RDS) approach and will include 5000 participants in 10 cities across Ukraine. Behavioral data will be collected using individual, structured self/interviewer-administered questionnaire. Biological data will be collected using rapid testing algorithms for HIV, hepatitis C and syphilis. Participants with confirmed new positive test results will be referred to health care institutions for follow-up and care. Dry blood spot (DBS) samples will be collected to assess recency of HIV infection and viral load.

[figure not shown]
The survey “Integrated Biological and Behavioral Survey among People Who Inject Drugs” will be conducted in 2023, as a component of a SILTP “Strengthening HIV Treatment, Laboratory Services, Medication Assisted Therapy, and Program Monitoring in Ukraine under the President's Emergency Plan for AIDS Relief (PEPFAR)” implemented by the State Institution “Public Health Center of the Ministry of Health of Ukraine” (the PHC) with the support from the US Centers for Disease Control and Prevention (CDC). (Cooperative agreement number - NU2GGH002375).

¹ https://data.unaids.org/publications/irc-pub01/jc370-2ndgeneration_en.pdf

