4.4 Sample size and power calculation

To calculate the sample size, a design effect was empirically estimated in the 2020 IBBS data set using the Gile's SS estimator based on the actual network size in "RDS" package in R v.4.0.5 (Table).

	HIV prevalence				Viral suppression			
	Est.	95% CI LL	95% CI UL	D.Eff.	Est.	95% CI LL	95% CI UL	D.Eff.
Bila Tserkva	16.1%	10.2%	21.9%	3.11	77.7%	66.6%	88.7%	2.39
Dnipro	26.5%	19.8%	33.2%	2.78	68.8%	54.8%	82.6%	3.56
Ivano-Frankivsk	9.3%	5.8%	12.9%	2.61	89.3%	82.8%	96.4%	1.44
Kirovohrad	10.2%	7.0%	13.4%	1.80	74.2%	61.4%	87.3%	2.70

Kryvyi Rih	21.9%	16.1%	27.7%	2.13	70.6%	59.9%	81.1%	1.72
Kyiv	18.2%	12.9%	23.5%	3.27	86.0%	77.0%	95.0%	2.96
Mariupil	30.5%	25.3%	35.6%	2.11	80.9%	72.7%	89.1%	2.21
Mykolaiv	33.2%	27.5%	38.9%	2.88	76.4%	68.3%	84.4%	2.49
Odessa	21.2%	15.3%	27.1%	2.50	80.7%	73.4%	87.9%	1.31
Kharkiv	7.5%	4.1%	11.0%	2.12	90.9%	91.0%	91.0%	-
Khmelnytskyi	29.7%	23.7%	35.7%	2.47	81.9%	74.3%	89.3%	1.91
Cherkasy	38.4%	31.4%	45.6%	2.43	86.5%	80.1%	93.0%	1.61

As shown, the design effect for HIV prevalence ranges from 1.8 to 3.3, and for viral suppression from 1.3 to 3.6. Therefore, a conservative value of 3.0 is used for the following sample size calculation.

The calculation was made for *the single sentinel cluster* sample, with expected HIV prevalence of 21% and 44% viral suppression (combined weighted estimate using 2020 round data for 5 cities and 2017 data for Lviv). Based on the simple asymptotic CI formula,¹¹ 0.05 probability of type I error, anticipated 5% of missing data, and 14% desired precision level for the viral suppression indicator (e.g. 44±7%), the resulting sample size should be 2914.

[figure not shown]
In order to simplify trend analysis across rounds, the total sample will be distributed evenly across participating cities, yielding a rounded target sample size of 500 in each city. This result corresponds to the standard universal sample size used in the US NHBS-IDU.¹² At the city level, assuming the design effect of 3.0 and 5% of missing data (e.g. incomplete data entry, entry errors), a sample size of 500 will provide ~16% precision for a maximally-conservative estimated prevalence for any indicator – 50% (i.e. 50±8%, the interval will be narrower for proportions closer to extremes, either 0 or 100%).

The same target sample size will be used for each additional city (outside the sentinel cluster).

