9.4 Trend analysis

To analyze the changes in key outcomes of interest across rounds, the final dataset may be merged with datasets from previous rounds. Only cities that participated in each analyzed round will be included. Combined weights (a product of RDS weight and city sample size weight OR the city population size, when becomes available) will be calculated and applied in the trend analyses. The significance of trend will be tested using two methods: (a) Mantel-Haenszel test of trend, used in the previous studies¹³, and (b) regression models with the survey round as an ordinal independent variable. Additionally, comparison between two consecutive rounds using Pearson's chi-square tests.

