16.0 Annex. Selection of cities for the 2023 PWID IBBS

Region	City	PWID population 2017	HIV prevalence 2020	Viral suppression 2020	Number of IBBS rounds participated 2007-2020	Selection for the 2023 round
AR Crimea	Simferopol				6	
Vinnytsia	Vinnytsia	5400			5	
Volyn	Lutsk	1800			6	
Dnipropetrovsk	Dnipro	20100	23.0%	33.0%	8	sentinel
Dnipropetrovsk	Kryvyi Rih	13300	23.7%	14.1%	4	
Donetsk	Donetsk	11700			6	
Donetsk	Mariupil		29.4%	38.8%	2	
Zhytomyr	Zhytomyr	2600			5	
Zakarpattia	Uzhgorod	1400			5	
Zaporizhzhia	Zaporizhzhia	7900			5	additional
Zaporizhzhia	Melitopol	3400			1	
Ivano-Frankivsk	Ivano-Frankivsk	2000	10.8%	61.5%	6	
Kyiv	Bila Tserkva	2700	15.9%	43.3%	5	
Kyiv	Vasylkiv	1300			3	
Kyiv	Fastiv	1200			3	
Kirovohrad	Kropyvnytskyi	5900	11.9%	28.4%	7	
Lugansk	Lugansk				5	
Lugansk	Sieverodonetsk	900			2	
Lviv	Lviv	6400			5	sentinel
Mykolaiv	Mykolaiv	8500	27.3%	56.4%	8	
Odesa	Odesa	21700	20.4%	42.1%	7	sentinel
Poltava	Poltava	4300			6	
Rivne	Rivne	3500			5	additional
Sumy	Sumy	7800			6	
Ternopil	Ternopil	3200			5	
Kharkiv	Kharkiv	9900	7.1%	20.0%	7	sentinel
Kherson	Kherson	4500			6	additional
Khmelnytskyi	Khmelnytskyi	5200	27.5%	53.2%	6	
Cherkasy	Cherkasy	4600	34.6%	62.1%	8	sentinel
Chernivtsi	Chernivtsi	3700			5	
Chernihiv	Chernihiv	4400			5	additional
Kyiv City	Kyiv City	33700	16.6%	39.6%	8	sentinel
Sevastopol	Sevastopol	6600			4

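### Section 9.2 omits city weights from pooled estimates because city samples are equal, but equal samples from cities of very unequal size are the reason to weight

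*Protocol*

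**What the plan says.** Section 1.0 says that the survey "will include 5000 participants in 10 cities across Ukraine". Under section 4.4 "the total sample will be distributed evenly across participating cities", "yielding a rounded target sample size of 500 in each city".

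Section 9.2 sets the rule for pooling: estimates for the total sample carry the RDS weights but "will not be additionally weighted due to the equal sample size in each city". Its next sentence adds that, once the population size calculation is available, "additional weighting by population size in each city will be done to obtain estimates for the entire city sample for key variables".

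Section 9.4 defines the trend-analysis weights as "a product of RDS weight and city sample size weight OR the city population size, when becomes available", and uses only cities that took part in every round analysed.

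The Annex (section 16.0) lists 2017 PWID sizes for all ten cities. The Kyiv row reads "Kyiv City Kyiv City 33700 16.6% 39.6% 8 sentinel"; Rivne has 3,500. Section 13.2 promises a brief report with aggregated HIV indicators within two months of data collection.

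**The concern.** A fixed sample per city makes each participant in a large city stand for many more people than one in a small city. Pooling without a city weight then estimates an average over cities, not a proportion of PWID. Equal city samples cause this problem, so they cannot be a reason to skip the weight.

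The pooled HIV prevalence and viral suppression feed modelling and international reporting (sections 3.0 and 13.2). If equal-weight figures go out first and size-weighted figures follow, two totals for the same survey will circulate, and the protocol does not say which one is primary.

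**Working it through.** **1. The plan's own sample size.** Section 4.4: viral suppression 44%, half-width 7 points, design effect 3.0, HIV prevalence 21%, 5% missing.

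- HIV-positive needed: 3 × 1.96² × 0.44 × 0.56 / 0.07² = 579.5
- Total: 579.5 / 0.21 / 0.95 = 2,905

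The plan states 2,914, so its figure reproduces to within 0.3%. It contains no allowance for unequal city weights.

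**2. Sampling fractions and shares (Annex, 2017 sizes).** Kyiv 33,700 / 500 = 67.4; Rivne 3,500 / 500 = 7.0; ratio 33,700 / 3,500 = 9.6. The ten cities, with Vinnytsia in place of Kherson as in section 4.3, total 117,600. Kyiv holds 33,700 / 117,600 = 28.7% and Rivne 3.0%; each gets 10% without city weights.

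**3. Effect in the five sentinel cities that have 2020 values.** Lviv has none in either table.

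| City | N (2017) | HIV, Annex | VS, Annex | HIV, 4.4 | VS, 4.4 |
|---|---|---|---|---|---|
| Kyiv | 33,700 | 16.6% | 39.6% | 18.2% | 86.0% |
| Dnipro | 20,100 | 23.0% | 33.0% | 26.5% | 68.8% |
| Odesa | 21,700 | 20.4% | 42.1% | 21.2% | 80.7% |
| Kharkiv | 9,900 | 7.1% | 20.0% | 7.5% | 90.9% |
| Cherkasy | 4,600 | 34.6% | 62.1% | 38.4% | 86.5% |

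HIV prevalence: equal weight Σp/5; population weight ΣNp/ΣN, with ΣN = 90,000. Viral suppression (VS) among HIV-positives: equal weight Σpv/Σp; population weight ΣNpv/ΣNp.

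- HIV, Annex: 1.017/5 = 20.3%; 16,938.5/90,000 = 18.8%. Gap 1.5 points.
- HIV, section 4.4: 1.118/5 = 22.4%; 18,569/90,000 = 20.6%. Gap 1.7 points before rounding.
- VS, Annex: 0.4566/1.017 = 44.9%; 6,734/16,938.5 = 39.8%. Gap 5.1 points.
- VS, section 4.4: 0.9103/1.118 = 81.4%; 14,855/18,569 = 80.0%. Gap 1.4 points.

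**4. Sensitivity to Lviv.** Assume a Lviv prevalence between 5% and 40% and use Annex values for the other five. At 5% the six-city figures are 17.8% equal-weighted and 17.9% population-weighted, so the gap vanishes. At 40% they are 23.6% and 20.2%.

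**5. Precision under population weights.** Kish factor = kΣN²/(ΣN)².

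- Six sentinel cities (N in thousands): 6 × 2,170.72 / 96.4² = 1.40
- Ten cities: 10 × 2,293.90 / 117.6² = 1.66

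Expected HIV-positives with data in the sentinel cluster: 3,000 × 0.95 × 0.21 ≈ 598.

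- Design effect 3.0: 1.96 × √(3.0 × 0.2464 / 598) = 6.9 points
- Design effect 3.0 × 1.40 = 4.2: 1.96 × √(4.2 × 0.2464 / 598) = 8.2 points

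As a check, the factor among HIV-positives in the five cities (Annex prevalence) is Σp × ΣN²p / (ΣNp)² = 1.017 × 391.79 / 16.9385² = 1.39, so 1.40 is a fair stand-in.

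**The case against.** The strongest reply is that the protocol already plans the remedy. The sentence after the disputed one commits to population-size weighting. The key variables are described broadly at the start of section 9.2 and include infection prevalence and the treatment cascade. A reader might infer that pooled estimates stay unweighted for good; the text does not support that. This part of the reply stands and narrows the point.

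Other stronger readings also fail:

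- **Bias toward small, high-prevalence cities.** Five of the ten cities have no 2020 values. Among the other five, the smallest (Cherkasy) has the highest prevalence and the next smallest (Kharkiv) the lowest.
- **A five-point error in viral suppression.** That size comes from the Annex; the section 4.4 table gives 1.4 points.
- **A spurious trend from changing weights.** Section 9.4 allows two kinds of city weight, but nothing says that different rounds would get different kinds.
- **No total for the sentinel cluster.** Section 9.2 does not define the total sample. Section 4.4 uses that term with 629 people living with HIV, and 629/0.21 ≈ 2,995, which is six cities of 500.
- **A brief report that is certain to be unweighted.** No date is set for the size estimates, and the timeline has no separate row for them. It is a possibility only.

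It can also be said that waiting for 2023 sizes is prudent given wartime migration, and that an average over sentinel sites is a legitimate summary. Both are fair. The first calls for a caveat on provisional weights, the second for a label. Neither rescues the stated reason.

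**Conclusion.** The point holds in limited form. The rationale in section 9.2 is wrong. Pooled figures produced before the size estimates arrive would be averages of cities without being called so. No pooled estimate is named primary.

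In the five-city illustration equal weighting raises HIV prevalence by 1.5 to 1.7 points, and viral suppression by 1.4 or 5.1 points depending on which of the protocol's two tables is used. The size and sign for the ten-city total cannot be derived from the document.

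This rests on three assumptions: RDS weights are normalised within city (not stated; weights scaled to city population would already carry size), the 2017 sizes still describe relative city size, and the Kish factor multiplies the design effect of 3.0. The sample size of 2,914 is not in dispute. The ±7 points attached to it does not describe the size-weighted estimate that the plan intends.

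**What to change.** In section 9.2:

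- Delete the equal-sample reason.
- State that RDS weights are normalised within city and multiplied by city PWID size, and name the result the primary pooled estimate.
- Use the Annex 2017 sizes provisionally, with a caveat for wartime migration, until the 2023 sizes are available.
- Label any equal-weight total as an average of cities.

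In section 9.4, require the same type of city weight for every round within one trend analysis.

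In section 4.4, add that under population weighting the sentinel viral-suppression half-width is about 8.2 points (Kish factor about 1.40).

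No fieldwork or sample size changes. The cost is wider pooled intervals than section 4.4 advertises, which the plan's own later weighting already implies, and a possible revision of early figures when the 2023 sizes replace those of 2017.
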